**Protocol Amendment Summary of Changes Table**

Document History		
Document	Version Date	Summary of Changes and Rationale
Original protocol	28 June 2019	Not applicable (N/A)
Amendment 1	19 May 2020	
Protocol Administrative Clarification Letters (PACLs) were incorporated:
 
 
• Women of Childbearing Potential (WOCBP) Contraceptive use after last study dose is updated from “a minimum of 28 days” to “at least 5 months” to follow the study’s single reference safety document (SRSD), which is the Humira label in Appendix 4.
 
• Typographic error corrected for white blood cell count, lymphocyte count and platelets lab tests listed in Exclusion Criteria 19.
 
• Updated instruction on empty drug containers in Sections 6.1.1 and 6.2. They need to be returned, not destroyed for investigational product accountability purpose.
 
• Text update in the protocol title: “interchangeability of” is replaced by “switching between”.
 
• Week 22 injection site updated to abdomen instead of abdomen or either upper front thigh to support primary data analysis in Schedule of Activities (SoA), Table 1, Sections 6.1.1 and 6.1.2.
 
• Alternative solutions that are only acceptable during the COVID-19 pandemic language have been added in SoA, Sections 6.2.1, 6.4, 7.1, 7.2 and Appendix 11.
 

Document History		
Document	Version Date	Summary of Changes and Rationale
		
Updated status of expecting PF-06410293 approval as a biosimilar to Humira from Food and Drug Administration (FDA) and regulatory agencies to approval for PF-06410293 as a biosimilar to Humira was received from the FDA in Sections 1.1, 2, 2.2 and 2.3.
 
 
Mention of marketing applications under review with other agency(s) is removed from Section 2.2.
 

		Corrected participant's age range from age of 18 and older to between age of 18 to 70 years in Section 1.1.
		Corrected definition for end of Treatment Period (TP) 4 to include Week 32 dose administration, and Safety Follow Up Period to begin after the last investigational dose at Week 32 in Sections 1.1 and 4.1.
		Added clarification in Table 1, Sections 1.1, 4.1 and 8.5 that the 2-week pharmacokinetic (PK) sampling period starts with Week 30 predose PK collection and ends with predose PK collection at Week 32.
		Added clarification in Section 1.1 that immune-related safety will be described for the safety population including injection site reactions, hypersensitivity, anaphylaxis and angioedema.
		CCI [REDACTED]
		Added utilization of home healthcare service as an option during the 2 week PK

Document History		
Document	Version Date	Summary of Changes and Rationale
		sampling period in SoA, Table 1 and Section 8.5.
		Clarified that only applicable adalimumab injection details will be recorded in the electronic Participant Dosing Log in SoA, Sections 6.1.1 and 6.4.
		
Clarifications made to the following inclusion/exclusion criteria to stay consistent with Humira label:
 
 
• Removal of Inclusion Criterion 7 as it is a duplication of Exclusion Criterion 14. Additionally, clarification is made to Exclusion Criterion 14.
 
• Clarification provided to Section 5.2, Exclusion Criteria 4c and Section 8.2.8 that confirmed positive HIV, Hepatitis B and Hepatitis C are excluded. More specifically, Hepatitis B DNA test has been added.
 
• Clarification provided on prohibited biologic therapy in Exclusion Criterion 13, Section 6.5 and Appendix 9 (Prohibited Concomitant Medication and Procedures).
 
• Added new Exclusion Criterion 18 that unstable dose of oral and intramuscular (IM) corticosteroid is prohibited. Updated Sections 6.5.2 and removed Appendix 9 (Oral Corticosteroid in FAP).
 

		Add clarification to Exclusion Criterion (#3) that active significant infection,

Document History		
Document	Version Date	Summary of Changes and Rationale
		eg, SARS-CoV2 (COVID-19) infection and any active infection considered to be clinically significant by the investigator should be excluded. Updates are also made in Sections 7.1.1 and 7.1.2.
		Language in Section 7.2 has been updated to follow Pfizer’s latest protocol template.
		Updated population for analysis in Section 9.3 and AE analysis in Section 9.4.2.1.
		Updated contraceptive requirements to follow Humira label for male participants Section 10.4.1. Additionally, removed text “highly” from highly effective contraceptive methods in Exclusion Criterion 24, Sections 5.3.1 and 10.4.4 to keep consistent with Humira label.
		Additional typographic errors were corrected and editorial changes provided, as deemed necessary, throughout the protocol.
		Blood sample volume was updated in Section 8.5
		Section 8.9 Immunogenicity Assessments have been added to follow Pfizer’s protocol template, as a result Section 8.5.1 in protocol (28 June 2019) has been reformatted to Section 8.9.1 in Amendment 1.

## 1. PROTOCOL SUMMARY

### 1.1. Synopsis

#### Short Title: A Comparative Study Between PF-06410293 And Humira in Combination with Methotrexate in Participants with Active Rheumatoid Arthritis

#### Rationale

Regulatory approval for PF-06410293 as a biosimilar to Humira was received from United States (US) FDA. The purpose of conducting this trial is to support the application for the interchangeability designation with the FDA, not to re-establish “PK equivalence” between licensed Humira and PF-06410293. The objectives and design of this study are consistent with recommendations for establishing interchangeability (IC) found in the corresponding guidance.

A designation of IC for an approved biosimilar drug is granted by the US FDA based on information demonstrating that ‘the risk in terms of safety or diminished efficacy of alternating or switching between use of the biological product and the reference product is not greater than the risk of using the reference product without such alternation or switch’ (FDA Guidance, 2019). In reference to a biological product, interchangeability means that “the biological product may be substituted for the reference product without the intervention of the health care provider who prescribed the reference product”. This study has been designed with input from FDA to deliver sufficient information to support the interchangeability of PF-06410293 with the reference product, Humira.

#### Objectives, Estimands, and Endpoints

Objectives	Estimands	Endpoints
Primary:	Primary:	Primary:

 
To evaluate interchangeability of PF-06510293 and Humira by examining adalimumab steady-state pharmacokinetics in a switching arm (following 3 switches between Humira and PF-06410293) as compared to a non-switching arm (receiving only Humira).
 
	
 
Evaluate the equivalence of primary endpoints (maximum observed concentration (<math>C_{max}</math>) and area under the concentration-time curve over the dosing interval (<math>AUC_{\tau}</math>) obtained during the intensive PK sampling interval) between the switching arm and non-switching arm in participants who meet the PK population criteria, that include criteria for the number and timing of missing doses, availability of PK data, adherence to background therapy, and major protocol
 
	
 
<math>C_{max}</math> and <math>AUC_{\tau}</math> obtained during the intensive PK sampling interval.
 

	deviations related to PK assessment.	
Objectives	Estimands	Endpoints
Secondary:	Secondary:	Secondary:

 
To evaluate other serum adalimumab PK parameters in the switching arm and the non-switching arm.
 
To evaluate the overall safety and tolerability of the switching arm and the non-switching arm.
 
To evaluate immunogenicity of the switching arm and the non-switching arm.
 
	
 
Summarize other serum adalimumab PK parameters, including time at which <math>C_{max}</math> occurs (<math>T_{max}</math>), average concentration over the dosing interval (<math>C_{av}</math>), and apparent clearance (CL/F) obtained during the intensive PK sampling interval in participants who meet the PK population criteria, and predose concentration during multiple dosing (<math>C_{trough}</math>) obtained at scheduled PK sample timepoints in participants who meet the safety population criteria, for the switching arm and non-switching arm.
 
Summarize safety endpoints for the switching arm and non-switching arm in participants who meet the safety population criteria.
 
Summarize percent of participants with antidrug antibodies (ADA), and neutralizing antibodies (NAb) and ADA/NAb titers over time for the switching arm and non-switching arm in participants who meet the Safety population criteria.
 
	
 
Other serum adalimumab PK parameters, including <math>T_{max}</math>, <math>C_{av}</math>, and CL/F obtained during the intensive PK sampling interval and <math>C_{trough}</math> obtained at scheduled PK sample timepoints.
 
Safety measures characterized by type, incidence, severity, timing, seriousness and relatedness of treatment-emergent AEs and laboratory test abnormalities.
 
Percent of participants with ADA/NAb and ADA/NAb titers over time.
 

## Overall Design

This is an open-label, 2-arm, randomized, parallel-group study conducted to assess the impact of multiple switches between Humira and PF-06410293 on steady state adalimumab PK compared to the steady state PK of adalimumab following continuous dosing with Humira. This study is also designed to evaluate safety and immunogenicity after investigational product (IP) switching between the switching arm (Humira and PF-06410293), as compared with non-switching arm (Humira). For purposes of this

protocol, the treatment arm that includes switches between PF-06410293 and Humira will be referred to as the “switching” arm, while the treatment arm that comprises continuous Humira treatment will be referred to as the “non-switching” arm.

The study will include adult participants between the age of 18 and 70 years with moderate to severe rheumatoid arthritis (RA) who are on background methotrexate (MTX). This study has two arms and comprises 3 switches in the switching arm, which has a total of four treatment periods (TP).

- TP1 (Lead In Period) will begin with the first dose of investigational product Humira on Week 0 (Day 1) and conclude with the completion of Week 10 pre-dose assessments.
- TP2 will begin with the 1:1 randomization of the participants to either the switching arm or the non-switching arm at Week 10. Investigational product dosing for Week 10 will begin after the randomization process in the respective treatment arms and will conclude with the completion of Week 16 pre-dose assessments.
- TP3 will begin with investigational product dosing on Week 16, and conclude with the completion of Week 22 pre-dose assessments.
- TP4 will begin with investigational product dosing on Week 22 and continue through Week 30, where onsite investigational product dosing is scheduled at Weeks 22, 24, 26, 28, and 30, followed by a 2-week PK sampling period from Week 30 to Week 32. TP4 will conclude with end of treatment (EoT) assessments and final dose administration at Week 32.
- The 2-week PK sampling period starts with Week 30 predose PK collection and ends with predose PK collection on Week 32.
- Safety Follow-Up Period begins after the last investigational product dosing on Week 32, and concludes at completion of the Week 36 assessments. All participants (including early discontinuations) will be followed for at least 28 calendar days from the date of their last dosed investigational product. Week 36 safety follow up may be conducted via phone.

### **Number of Participants**

A maximum of approximately 420 participants will be enrolled into the study such that approximately 314 evaluable participants complete the study.

### **Intervention Groups and Duration**

The total duration of study participation is 36 weeks. Participants will receive investigational product for the first 30 weeks over 4 treatment periods, followed by a 2-week intense PK sample collection period, last investigational product dosing at the end of the PK sampling period and a 4 week safety follow up. The duration and details of each treatment period are described in the previous section.

Every participant will receive adalimumab 40 mg to be administered subcutaneously (SC) every 2 weeks; on-site injections will occur at the clinic during scheduled visits. The first injection is to be administered at the site under the supervision of the investigator or designee, where the participant and/or care giver will be assessed for their ability to administer adalimumab. Any issues may be reviewed at that time. The first injection should be an abdominal injection. Subsequently, the injection location may be the abdomen or upper front of either thigh, unless otherwise specified in the [Schedule of Activities \(SoA\)](#). Following the first injection at the site, the participant should select a day of the week to administer their investigational product injections at home every other week, on the same day, except on the weeks where an onsite visit is scheduled. Injections will occur during the scheduled visits under the supervision of the site's investigator or designee. Every effort should be made for participants to return for the scheduled visits and investigational product administration within the visit windows outlined in the [SoA](#) to support the PK endpoints of this study.

Please refer to [Section 6](#) for additional investigational product information.

#### **Data Monitoring Committee:**

This study will not use a data monitoring committee (DMC).

#### **Statistical Methods**

##### Pharmacokinetics

The serum concentrations between Week 30 and Week 32 will be analyzed for the PK population using standard non-compartmental analysis to estimate the PK parameters for each individual participant. The PK parameters: maximum observed concentration ( $C_{max}$ ), area under the concentration - time curve over the dosing interval ( $AUC_{\tau}$ ), time at which  $C_{max}$  occurs ( $T_{max}$ ), average concentration ( $C_{av}$ ), predose concentration during multiple dosing ( $C_{trough}$ ), and apparent clearance ( $CL/F$ ), and the serum concentrations will be summarized descriptively.

Interchangeability will be assessed by constructing the point estimate and the 90% confidence intervals (CIs) for the geometric mean ratio (GMR) for the primary endpoints  $C_{max}$  and  $AUC_{\tau}$ . Interchangeability will be established statistically if the 90% CI for the GMR is within (80.00%, 125.00%) for both endpoints. The GMR and CI will be obtained using analysis of variance (ANOVA) applied to log-transformed data, with terms for treatment and randomization stratification factors (weight categories).

##### Safety

Adverse Events will be summarized descriptively using Safety-TP1 population for Humira group in TP1 and using Safety-Randomized populations for switching arm and non-switching arm during TP2 through TP4.

[figure not shown]
[figure not shown]
### Immunogenicity

For the ADA (antidrug antibodies) and NAb (neutralizing antibodies) data, the percentage of participants with positive ADA and NAb will be summarized for the safety-randomized population by each visit in each Treatment Period. For participants with positive ADA and NAb, the magnitude (titer), time of onset, and duration of ADA and NAb response will also be described. In addition, immune-related safety will be described for the safety population including injection site reactions (ISR), hypersensitivity, anaphylaxis, and angioedema.

### Efficacy

This study will not evaluate efficacy.

## 1.2. Schema

● Adalimumab Switches in Switching Arm

TP = Treatment Period.

### 1.3. Schedule of Activities (SoA)

The SoA table provides an overview of the protocol visits and procedures. Refer to the [STUDY ASSESSMENTS AND PROCEDURES](#) section of the protocol for detailed information on each procedure and assessment required for compliance with the protocol.

The investigator may schedule visits (unplanned visits) in addition to those listed in the SoA table, in order to conduct evaluations or assessments required to protect the well-being of the participant.

Study related visits and procedures may be disrupted during the Coronavirus Disease 2019 (COVID-19) pandemic, please see [Appendix 11](#) for alternative solutions, if applicable.

Study Period	Screen	Treatment Period 1 (Lead In)			Treatment Period 2	Treatment Period 3	Treatment Period 4						Safety Follow up
		1	2 (BL)	3			4	5	6	7	8	9	
Visit Identifier	1	2 (BL)	3	4	5	6	7	8	9	10	PK Profile Phlebotomy 	11 (EOT/ET) 	12 
Study Week 	-6 to -1	0	4	10	16	22	24	26	28	30	30, 31	32	36
Study Day	-42 to -1	1	29	71	113	155	169	183	197	211	211 - 224	225	253
Visit Window in Days			±7	±7	±7	±7	±7	±7	±7	±7	[±1]	±1	+14
Informed Consent	X												
Inclusion/Exclusion Criteria	X	X											
Contraception check	X												
Medical History	X												
Demography	X												
Prior Treatments for RA	X												
HIV, Hepatitis B & C 	X												
FSH 	X												
Tuberculosis Test 	X												
Chest Radiography 	X												
Single ECG (12-Lead)	X												
Participant ID number (IWRS) 	X												
Randomization (IWRS) 				X									
Complete Physical Examination 	X											X 	
Vital Signs 	X	X		X								X	
Body Weight 	X	X		X 								X	

Study Period	Screen	Treatment Period 1 (Lead In)			Treatment Period 2	Treatment Period 3	Treatment Period 4						Safety Follow up
		1	2 (BL)	3			4	5	6	7	8	9	
Visit Identifier	1	2 (BL)	3	4	5	6	7	8	9	10	PK Profile Phlebotomy 	11 (EOT/ET) 	12 
Study Week 	-6 to -1	0	4	10	16	22	24	26	28	30	30, 31	32	36
Study Day	-42 to -1	1	29	71	113	155	169	183	197	211	211 - 224	225	253
Visit Window in Days			±7	±7	±7	±7	±7	±7	±7	±7	[±1]	±1	+14
Pregnancy Test 	X	X										X	
Contraception Verification		X											
Safety Laboratory	Hematology	X	X	X								X	
	Chemistry	X	X	X								X	
	Urinalysis	X	X	X								X	
Urine Drug screen	X												
ADA/Nab Samples 		X		X	X	X	X	X	X	X		X	
CCI													
Drug Concentration Samples 		X		X	X	X	X	X	X	X	X  (7 samples)	X	
Adalimumab SC Injection 		X	X	X	X	X	X	X	X	X		X	
Background Methotrexate and folic/folinic acid	X	X	X	X	X	X	X	X	X	X	X	X	X
Assessment of AEs 	X	X	X	X	X	X	X	X	X	X	X	X	X
Assessment of Concomitant Medications 	X	X	X	X	X	X	X	X	X	X	X	X	X

**Abbreviations:** ADA = Anti-drug Antibody; AE = Adverse Event; BL = Baseline; ECG = Electrocardiogram; EOT = End of Treatment Period; ET = Early Termination; FSH = follicle stimulating hormone; HCG = human chorionic gonadotropin; HIV = Human Immunodeficiency Virus; ID = Identification; IWRS = InteractiveWeb-based response system; Nab = Neutralizing antibody; PK = Pharmacokinetics; CCI; SC = Subcutaneous.

**Footnotes:**

1. Visits should occur when scheduled, within the time window indicated in the column headings. When a visit does not happen on the scheduled day within or outside the window, the next visit should still be on the initially scheduled calendar date to restore the original calendar. On investigational product dosing days, assessments and lab tests are to be performed prior to dosing unless otherwise stated. This will require special attention to ensure participants do not administer the corresponding visit's adalimumab injection prior to the clinic visit. Additional unscheduled assessments should be performed as clinically indicated.
2. Viral disease screening, including hepatitis screening (HBsAg, HBcAb, HBsAb, HCVAb and HCV RNA) and HIV screening (HIV-1 Ab and HIV-2 Ab). HIV screening (HIV-1 Ab and HIV-2 Ab) may be performed by the central lab or a local lab (if required by local regulations) at screening or within 6 weeks prior to the first dose of investigational product on Day 1.
3. Screening test for female participants who are amenorrheic for at least 12 consecutive months at the time of study screening with no alternative pathological or physiological cause. A serum FSH level within the central laboratory's reference range will confirm the participant's non-childbearing status.
4. Tuberculosis test will use QuantiFERON® (QFT) – TB Gold In-Tube Test and must be performed within 6 weeks prior to the first dose of investigational product on Day 1. Participants with positive or indeterminate screening QFT result must be re-tested with QFT – TB Gold In-Tube Test and referred to a specialist (eg, pulmonologist, TB specialist or infectious disease specialist) for further evaluation of latent or active TB or false positive QFT test result, unless they have past history of having been adequately treated with appropriate chemoprophylaxis for latent TB or have completed treatment for active TB previously, in which case re-testing is not required. Participants who test positive and are considered to have current latent TB can enroll in the study if they are on chemoprophylaxis for at least 4 weeks.
5. Chest radiography (lateral and posterior-anterior views) must be performed within a 12-week window prior to Screening. If a chest computed tomography (CT) exam (or an alternative chest imaging) is performed within 12 weeks prior to Screening, a chest x-ray is not required.
6. Individuals who do not meet the criteria for participation in this study (screen failure) within the 6 week screening period may be rescreened.
7. Participants completing Treatment Period 1 will be randomized into switching or non-switching treatment arms in a 1:1 ratio prior to dosing on Week 10, stratified based on 3 weight groups (Week 10 weight). Participants randomized to the non-switching arm will continue on Humira for the remainder of the study, and participants randomized to the switching arm will continue switching in each TP (TP2: PF-06410293; TP3: Humira; TP4: PF-06410293).
8. Complete physical exam (PE) of major body systems. Additional targeted PE may be performed during the study at the investigator's discretion, as indicated by signs and symptoms of ongoing AEs.
9. Vital signs include blood pressure, respiratory and pulse rate, body temperature, body weight, with height measured at Screening only. Blood pressure and pulse rate should be taken from the participant in the supine position after the participant has been resting quietly for at least 5 minutes.
10. Body weight (BW) for Randomization should use the one collected at Week 10. Every effort should be made to obtain BW at Week 10 prior to randomization, however, if the Week 10 BW is not available, Screening or Baseline BW (whichever is closest to Week 10 visit) may be used to randomize.
11. Pregnancy testing at Screening in female participants of childbearing potential by central lab serum HCG test. Pregnancy testing (HCG) after Screening will be performed locally using urine samples. Pregnancy testing may be repeated more frequently if required by IRB/ECs or local regulations, or if potential pregnancy is suspected.
12. Blood samples should be collected for ADA and NAb testing at the time when PK samples are also collected and prior to the next investigational product administration.

CCI

14. Please refer to [Table 1](#) (PK Sampling Table). **ALL PK samples will be collected prior to study dose (pre-dose)** at visits where onsite injection is scheduled. Blood samples for determination of adalimumab trough drug concentrations will be collected within 6 hours prior to the investigational product administration on Weeks 22, 24, 26, 28, and on Day 1 (time 0), Weeks 10 and 16 at a maximum of 48 hours prior to, but as close as possible prior to the next investigational product administration (ie, pre-dose). The 2-week PK sampling period starts with Week 30 predose PK collection and ends with Week 32 predose PK collection. Blood samples for determination of adalimumab drug concentrations for the 2-week PK profile will be collected starting with the Week 30 injection of investigational product (PK Profile Day 1): blood will be collected within 6 hours prior to investigational product administration. For the subsequent PK Profile Days, post-Week 30 dosing times for serum collections are 48 ( $\pm 4$ ) hrs on PK Profile Day 3, 72 ( $\pm 6$ ) hrs on PK Profile Day 4, 96 ( $\pm 8$ ) hrs on PK Profile Day 5, 144 ( $\pm 8$ ) hrs on PK Profile Day 7, 240 ( $\pm 24$ ) hrs on PK Profile Day 11, and 336 ( $\pm 24$ ) hrs on PK Profile Day 15. **Every effort should be made to draw samples within the scheduled time points.** The 2-week PK Profile collections may be completed using home health care service.
15. Investigational product will be administered by the participant, care giver or site personnel every other week using pre-filled syringes provided by the sponsor; on-site injections will occur during every scheduled visits after PK and ADA/NAb sample collection. The first SC injection should be administered by the participant while at the clinic under the supervision of the site's investigator or designee. Any issues may be reviewed at that time. The first injection must be an abdominal injection. Subsequently, the injection location may be the abdomen or upper front of either thigh. The first TP4 injection at Week 22 and injections at Weeks 24, 26, 28 and 30 (before starting the PK profile) must also be administered in the abdomen under the supervision of the site's investigator or designee. Applicable injection details (eg, date) will be recorded in the electronic Participant Dosing Log. Investigational product will be dispensed to the participant at each visit.
16. After 30 weeks of investigational product plus 2 weeks of PK profile participants are required to return for an end of treatment (EOT) visit at Week 32 where the last investigational product dose is scheduled, then will be followed up for final safety evaluation at Week 36, which may be a phone visit. Early terminated (ET) participants are required to return to the clinic as soon as possible after the last investigational product dose for an ET visit and safety phone follow up is also required at least 28 calendar days after the last investigational product. Additional targeted PE may be performed at the ET and/or post-treatment follow up visits at the investigator's discretion, as indicated by signs and symptoms of ongoing AEs.
17. The time investigational product period for actively eliciting and collecting AEs and SAEs ("active collection period") for each participant begins from the time the participant provides informed consent, through and including a minimum of 28 calendar days after the last administration of the investigational product. Week 36 safety follow up may be conducted via phone.
18. Concomitant medications will be routinely collected from the time the consent form is signed through the final study visit/contact. If a participant discontinues early, concomitant medications must be followed for 28 calendar days after last dose of investigational product. Week 36 safety follow up may be conducted via phone.

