**Table 1. PK Sampling Table**

Study Period	Treatment Period 1		Treatment Period 2	Treatment Period 3	Treatment Period 4									
	Day 1 Abd Inj	Wk 10 Abd Inj	Wk 16 Abd Inj	Wk 22 Abd Inj	Wk 24 Abd Inj	Wk 26 Abd Inj	Wk 28 Abd Inj	Wk 30 Abd Inj	PK Day 3	PK Day 4	PK Day 5	PK Day 7	PK Day 11	Wk 32
PK Profile Day								1	3	4	5	7	11	15
Time (h) Post-Dose	0 a,b	0 a,b	0 a,b	0 a,b	0 a,b	0 a,b	0 a,b	0 a,b	48	72	96	144	240	336 a
PK Tolerance Window (h) d	-48	-48	-48	-6	-6	-6	-6	-6 c	±4 c	±6 c	±8 c	±8 c	±24 c	±24 c

- Predose PK sample.
- Injection on-site.
- PK sample must fall within the PK sampling time window for the participant to be Per Protocol (for the primary endpoint).
- Blood samples for determination of adalimumab trough drug concentrations will be collected within 6 hours prior to the investigational product administration on Weeks 22, 24, 26, 28, and on Day 1 (time 0), Weeks 10 and 16 at a maximum of 48 hours prior to, but as close as possible prior to the next investigational product administration (ie, pre-dose). The 2-week PK sampling period starts with Week 30 predose PK collection and end with Week 32 predose PK collection. Blood samples for determination of adalimumab drug concentrations for the 2-week PK profile will be collected starting with the Week 30 injection of investigational product (PK Profile Day 1): blood will be collected within 6 hours prior to investigational product administration. For the subsequent PK Profile Days, post-Week 30 dosing times for serum collections are 48 (±4) hrs on PK Profile Day 3, 72 (±6) hrs on PK Profile Day 4, 96 (±8) hrs on PK Profile Day 5, 144 (±8) hrs on PK Profile Day 7, 240 (±24) hrs on PK Profile Day 11, and 336 (±24) hrs on PK Profile Day 15. **Every effort should be made to draw samples within the specified time windows.** The 2-week PK Profile collections may be completed using home health care service

Abbreviations: Abd = abdominal; h = hour; Inj = injection; PK = pharmacokinetic; Wk = week.

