## 8.5. Pharmacokinetics

Blood samples of approximately 6 mL, to provide a minimum of 1 mL of serum per aliquot (2 total), will be collected for measurement of serum concentrations of adalimumab as specified below.

- Samples for determination of adalimumab trough drug concentrations will be collected within 6 hours prior to the investigational product administration on Weeks 22, 24, 26, 28, and on Day 1 (time 0), Weeks 10 and 16 at a maximum of 48 hours prior to, but as close as possible prior to the next investigational product administration (ie, pre-dose).
- Primary endpoint data will be supported by the determination of adalimumab drug concentrations for the 2-week PK Profile.
- The 2-week PK sampling period starts with Week 30 pre-dose PK collection and ends with Week 32 pre-dose PK collection.
  - Pre-dose PK collection at Week 30/PK Profile Day 1, the blood sample will be collected within 6 hours prior to investigational product administration.
  - For the subsequent PK Profile Days, post-Week 30 dosing times for serum collections are:
    - 48 ( $\pm 4$ ) hrs on PK Profile Day 3,
    - 72 ( $\pm 6$ ) hrs on PK Profile Day 4,
    - 96 ( $\pm 8$ ) hrs on PK Profile Day 5,
    - 144 ( $\pm 8$ ) hrs on PK Profile Day 7,
    - 240 ( $\pm 24$ ) hrs on PK Profile Day 11, and
    - 336 ( $\pm 24$ ) hrs on PK Profile Day 15; before Week 32 dosing.

The 2-week PK Profile collections may be completed using home health care service. Please reference [Table 1. PK Sampling Table](#). In order for participant's PK Profile to be included in the primary analysis **every effort should be made to draw samples within the specified time windows**.

Serum samples for PK assessment will be analyzed using a validated enzyme linked immunosorbent assay (ELISA) to quantitatively measure concentrations of Humira and PF-06410293.

For detailed PK sample collection and processing instructions, please see the study laboratory manual.

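### With Week 30 at Day 211±7 and Week 32 held at Day 225±1, the Week 32 visit draw can meet its 336±24 h window on only 5 of 15 permitted Week 30 days

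*Protocol*

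**What the plan says.** **Visit days and windows.** In the Schedule of Activities (SoA, protocol Section 1.3), the row "Visit Window in Days" gives Week 30 (Day 211) ±7 days, Week 32 (Day 225) ±1 day and Week 36 (Day 253) +14 days.

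**Calendar rule.** SoA footnote 1 covers a visit that is off its scheduled day, whether or not it stayed inside its window: "the next visit should still be on the initially scheduled calendar date to restore the original calendar". No exception is written for the step from Week 30 to Week 32.

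**Last profile sample.** SoA footnote 14 says: "The 2-week PK sampling period starts with Week 30 predose PK collection and ends with Week 32 predose PK collection". Table 1 times that sample from the Week 30 dose, at "336 (±24) hrs on PK Profile Day 15". Section 8.5 requires it ahead of the next injection: "hrs on PK Profile Day 15; before Week 32 dosing". Footnote 14 also allows a home draw: "The 2-week PK Profile collections may be completed using home health care service".

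**Consequence of a mistimed sample.** Table 1, footnote c: "PK sample must fall within the PK sampling time window for the participant to be Per Protocol (for the primary endpoint"). Section 8.5 ties timing to the "PK Profile to be included in the primary analysis" only as something sites should try to achieve. The PK population in protocol Section 9.3 and SAP Section 4 has no sampling-window criterion. It excludes participants for missed samples that materially affect the parameters, or for major PK-related deviations judged by the study team. It states that the Week 32 dose may be missed or incomplete.

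**The concern.** The sample is timed from the actual Week 30 dose, while the visit at which it is due is timed from the original calendar. The Week 30 visit may move by 7 days either way, but Week 32 may not move with it. A site that stays inside every stated visit window and follows footnote 1 can therefore be unable to take the last primary-endpoint sample in its own window. The dosing rules in Sections 6.1.1 and 6.4 point the same way: after a late dose, the next one is given on schedule.

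What is at stake is the avoidable loss or mistiming of some AUCtau profiles, together with doubt about whether such a profile counts. Table 1 footnote c uses a 'Per Protocol' status that neither document defines, so it could set aside a profile that Section 9.3 and SAP Section 4 would keep.

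**Working it through.** **Inputs**
- Week 30 dose on Day 211 + d, with d = −7 to +7: Days 204 to 218, 15 permitted days (SoA).
- Week 32 visit on Day 225 + e, with e = −1, 0 or +1: Days 224 to 226 (SoA).
- Last sample 312 to 360 h after the Week 30 dose, taken before the Week 32 dose (Table 1, Section 8.5).

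**The plan's own figures.** On the nominal days, (225 − 211) × 24 = 336 h, as stated. The sample size in Section 9.2 also reproduces. With CV 55%, the log SD is √ln(1 + 0.55²) = 0.514. With 157 evaluable per arm and a GMR of 1.05, power is 91.1% for one endpoint and 84.9% for both at correlation 0.5 (stated 85%). Also 314/0.75 = 419 (stated about 420). Nothing here disputes those numbers.

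**Elapsed time at the Week 32 visit** = 24 × (14 + e − d) hours.

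| Week 30 offset d (Day) | Hours at Day 224 / 225 / 226 | Visit draw in window? | Separate draw before the Week 32 dose in window? |
|---|---|---|---|
| −7 (204) to −3 (208) | 480/504/528 to 384/408/432 | No | Yes |
| −2 (209) | 360/384/408 | Yes | Yes |
| −1 (210) | 336/360/384 | Yes | Yes |
| 0 (211) | 312/336/360 | Yes | Yes |
| +1 (212) | 288/312/336 | Yes | Yes |
| +2 (213) | 264/288/312 | Yes | Yes |
| +3 (214) | 240/264/288 | No | No |
| +4 (215) | 216/240/264 | No | No |
| +5 (216) | 192/216/240 | No | No |
| +6 (217) | 168/192/216 | No | No |
| +7 (218) | 144/168/192 | No | No |

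- Visit draw: d = −2 to +2, so 5 of 15 days.
- Separate home draw, which needs only that the Week 32 dose is not before 312 h: d = −7 to +2, so 10 of 15 days.
- With Week 32 exactly on Day 225, as footnote 1 reads literally, the counts are 3 of 15 (d = −1 to +1) and 9 of 15 (d = −7 to +1).
- For d = +3 to +7, a Week 32 dose on Day 226 comes 24, 48, 72, 96 and 120 h before the sample window opens at 312 h. Clock time does not help in practice: Day 214 would need a full 24 h swing between dose and draw times.
- For d = +7, the 240±24 h sample is caught too, since 192 h is below 216 h.

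**Ways out within the documents for a late dose.** With d = +3 to +7, 312 h falls on Days 227 to 231 and 336 h on Days 228 to 232. These days are 2 to 7 days after Day 225. The sample is obtainable if the Week 32 dose is held back that long or omitted.

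**After the fix.** Week 32 = Day 211 + d + 14 + e, so elapsed time is 24 × (14 + e) = 312, 336 or 360 h for every d: 15 of 15 days. Week 32 runs from Day 217 to Day 233, at most 8 days from Day 225. Follow-up: 233 + 28 = Day 261, inside the Week 36 window of Days 253 to 267; at the early end, 253 − 217 = 36 days.

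**Frequency (assumed; the documents give none).** If Week 30 were 3 or more days late in 1%, 5% or 10% of 314 evaluable participants, about 3, 16 or 31 profiles would be affected. The planned allowance is 420 − 314 = 106.

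**The case against.** **The sample is not necessarily lost.** Section 9.3 and SAP Section 4 let the Week 32 dose be missed without affecting the PK population. Sections 6.1.1 and 6.4 accept a dose up to 7 days late, although as a remedy for non-compliance, and Section 7.1.1 words its late-dose instruction for Treatment Periods 1 to 3 and the first two doses of Treatment Period 4. This stands. A reader might infer that a Week 30 dose 3 to 7 days late always spoils the profile. The documents do not support that; it follows only if the Week 32 dose is given on Day 225±1. What remains is that holding the dose back breaks footnote 1 and the Week 32 window, and no text tells a site to do so.

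**A sensible site would treat Week 32 as PK Profile Day 15.** Table 1 is specific and mandatory in tone, while footnote 1 is general and advisory. The 10 of 15 count already needs the profile column (Days 211 to 224) to be read as running from the actual dose, so the next column could be read that way too. This is a fair account of what many sites would do. It resolves the conflict by choosing between two written rules, and the protocol does not say which prevails.

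**Counting days is not counting participants.** This also stands. Footnote 1 stops earlier slips from accumulating, and the protocol stresses on-schedule dosing in Treatment Period 4.

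**The population rule is workable.** The PK population is the operative set in both documents, its deviation list is open-ended, and membership independent of PK results is settled before database release. One primary endpoint is enough for inclusion, and Cmax is not shown to be lost. So the 'Per Protocol' note is mainly a wording matter. SAP Section 5.3.2 does mention sampling-time deviations, but only for summary tables and mean-profile plots.

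**Conclusion.** The windows conflict as written. A draw at the Week 32 visit can be in window on 5 of 15 permitted Week 30 days, or 10 of 15 if a separate home draw is allowed. When the Week 30 dose is 3 to 7 days late and the Week 32 dose is given within its ±1 day, the last primary-endpoint sample cannot be in window: it comes at most 288, 264, 240, 216 or 192 h after dosing. Delaying or omitting the Week 32 dose is the only escape; the PK population rule tolerates it, but nothing instructs it.

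The counts assume whole calendar days and the full ±1 day at Week 32, which is lenient to the plan. A reader might infer that two thirds of profiles are at risk, that the arms would differ, or that power falls below 85%. None of that follows. The counts are days, not participants; the frequency of late Week 30 doses is not given; the same windows apply to both arms; and the 25% non-evaluable allowance may cover any loss. The point merits a change because following a stated rule can mistime a primary-endpoint sample and the remedy is cheap.

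**What to change.** 1. In SoA footnote 1, exempt the Week 30 to Week 32 interval. Set Week 32 (visit, predose sample and dose together) at the actual Week 30 dose +14±1 days, in place of Day 225±1. All 15 permitted Week 30 days then give 312 to 360 h.
2. As a secondary wording alignment, replace the 'Per Protocol' note in Table 1 with a reference to the PK population in Section 9.3 and SAP Section 4.

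**Cost.** The change is to one footnote, one visit window and one table note. Some Week 32 visits would fall off the original calendar, by at most 8 days. The Week 36 window (Day 253 to 267) can stay, since the latest 28-day point is Day 261. For a late Week 32, the existing 28-day minimum must decide the Week 36 date, because nominal Day 253 would be only 253 − 233 = 20 days after a Day 233 dose.
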